Protocol Title **A study to assess change in weight over six months in Prader-Willi Syndrome**

Date **February 22, 2018**

Principal Investigator [name].
Director of Research Programs
Foundation for Prader-Willi Research
[contact]
[contact]

Co-Investigators [name].
Associate Director of Translational Research Programs
Foundation for Prader-Willi Research
[contact]
[contact]

[name].
Associate Director of Research Programs
Foundation for Prader-Willi Research
[contact]
[contact]

Sponsor Name Foundation for Prader-Willi Research (FPWR)
[name]
[name]

Sponsor Study Number 2018_01

Confidentiality Statement: Information contained within this document is not to be disclosed in any way without the prior permission of the Principal Investigator.

I. Objectives

The primary objectives of the study are:

1. Perform a real-world study of weight changes over 6 months in PWS children and adults aged 12 and over.
2. Study factors that could directly or indirectly affect weight change such as diet, medication, food access and environment.
3. Collect data on participant height change over 6 months to calculate body mass index (BMI)

II. Background and Introduction

Prader-Willi syndrome (PWS) is a complex neurodevelopmental disorder resulting from disruption of an imprinted region of chromosome 15 (15q11.2-q13). PWS has an estimated incidence of 1:15,000-1:30,000 births worldwide, and equally affects males and females of all ethnicities. PWS

is characteristically associated with feeding difficulties and failure to thrive in infancy and early childhood, followed by the development of excessive eating (hyperphagia), intense food seeking behavior, and morbid obesity. Additional features of PWS include poor muscle tone and strength (hypotonia), hypogonadism, osteoporosis, scoliosis, infertility, delayed motor and language development, impaired cognition, sleep abnormalities, behavioral challenges including tantrums, obsessive compulsiveness and skin picking, and psychiatric illness in adulthood. The phenotype exhibits a broad spectrum of severity.

The incidence and natural history of several PWS symptoms are poorly defined. Gathering data on these is essential not only to understand the development and severity of each symptom without relying on anecdotal evidence, but also to appropriately direct therapeutic efforts and clinical trials.

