For this study, we will gather and analyze data on changes in body weight over a 6-month interval, roughly the time frame for a clinical trial, for individuals aged 12 and over to focus on age groups that are likely to be recruited in hyperphagia trials. It has previously been shown that weight changes in PWS may depend on age- and nutritional stages (Miller et al 2011), however, larger datasets across different age groups, with frequent measurements, are required to fully understand real world data regarding weight gain and obesity in PWS.

Weight may also be influenced by living situation, diet, medication and access to food. Therefore, we will also survey participants on diet and medication changes and food access, and study the extent to which these may play a role in any observed weight change.

Participants will be recruited from the U.S. and Canada through patient advocacy websites, Facebook and email. Interested participants will sign an informed consent prior to enrolling in the study.

III. Study Design

- We will utilize a commercially available text messaging based clinical app called Mosio (HIPAA and CFR Part 11 compliant) to collect data. (www.mosio.com)
- We will recruit up to n=300 participants. We expect to be able to recruit this number over 1-2 months prior to data collection (6 months).
- The study is expected to last 9 months, with 2 months for recruitment and start up, and 7 months for data collection.
- Mosio will create "Storylines"- a series of questions/surveys, that will be sent at pre-scheduled intervals, as and when participants sign-up.

Data to be collected:

1. Initial Survey at baseline only

- Was PWS diagnosis made by blood test.
- Gender
- Age
- Does the person receive growth hormone (GH) therapy? If yes, what age was therapy initiated? If no, were they ever on GH therapy? Age at initiation and how long were they on it.

- In the past 6 months, approximately how often did you weigh your child with PWS?
daily, weekly, monthly, less than monthly, only at doctor visits.
2. **Weight**- Once a week, every week, for 6 months. Participants will be sent a pre-scheduled text message reminder to weigh in and send a text response with the participant's weight.
 3. **Survey**-At 3 months and 6 months participants will answer a survey-
 1. Has there been any change in the living situation for the person with PWS in the last 3 months (example: moved, change in primary caregiver, illness in the family etc.? Y/N

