 2. To your knowledge has access to food at home or outside the home increased/decreased/stayed the same for the person with PWS?
 3. Has the activity level in the last 3 months increased/decreased/stayed the same for the person with PWS?
 4. Has there been medication change in the last 3 months for the person with PWS? Y/N
If yes-
Please list drug- and select start/stop/increased dose/decreased dose. Will provide option to list more than one drug.
 5. Please record participant's height.

Data will be stored in a secure database. Researcher will be given a log-in and have access to patient data throughout the course of the study.

IV. Duration of study

Study is expected to last 9 months with 3 months for recruitment followed by 6 months of data collection.

V. Eligibility and Recruitment of Participants

a. Inclusion Criteria

Male and female individuals diagnosed with PWS, 12 years and older.

b. Exclusion Criteria

- younger than 12
- non-PWS

c. Sample Size

Target sample size is 300 participants for this study

d. Recruitment of Participants

Participants will be informed of the study via website and social media outlets. These include patient advocacy websites, email, and the Global PWS Registry.

VI. Process of Obtaining Consent

Submission of information by participant or their representative: Participants will be provided details about the study, which will be posted on patient advocacy websites, Facebook, email and other social media outlets. They will be provided contact information and given every opportunity to read, understand and ask questions about the study via electronic means or phone. A consent form will be created on SurveyMonkey and a link to the consent form will be included with recruitment materials.

If they wish to participate in the study, participants or their parent/representative will be directed to an electronic informed consent form where they will be asked to review and sign an informed consent. Individuals providing consent will be asked to confirm that s/he is the participant or legally authorized representative of the participant. Consent from a legally authorized representative is required for participants who are minors or who are over the age of 18 but unable to provide informed consent. Because individuals with PWS have some degree of intellectual disability, the ability to provide consent will depend on the cognitive ability of the individual.

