A copy of the completed consent form will be made available to all participants.

VII. Data Analysis and Reporting

The following analyses are planned

1. Trends in weight and BMI change over 6 months.
2. Description of factors that could affect weight and BMI in this group, including food access, change in living situation, physical activity and medication.

VIII. Facilities and Performance Sites

This study will use mobile health technology. Interested participants will sign an informed consent and provide a mobile phone number on which they are able to send and receive text messages. FPWR will assign each participant a unique, random, study-related ID, not linked to any identifying information (eg. fpwr2018_001). Only this unique ID will be used on the Mosio platform. The key to the IDs will only be available to researchers associated with this study. Once registered, participants will receive text messages and surveys at pre-determined intervals on their mobile phones (discussed above) and will respond directly via text. Mosio will store all data on a secure server and provide investigators a login to the site. Only study personnel will be able to access the data.

IX. Potential Benefits

There is no direct benefit to the patient from participating in the study. As mentioned above, real-world studies are essential in PWS to understand the natural progression of the disease. At the end of the study, participants will receive a personalized chart detailing their weight progression over the course of the study.

X. Potential Risks, Discomforts, Inconveniences, and Precautions

Participation in the study presents minimal risks to its participants. The greatest risk is loss of confidentiality of personal health information.

XI. Risk/Benefit Analysis:

This is a minimal risk study without direct benefits to the individual. There are no risks of physical harm associated with participation in the study. While every effort will be made to keep data confidential there is a potential risk of a breach of confidentiality of medical information and associated privacy of the participants. This risk will be minimized by storing data on a secure server. Only authorized study personnel will have access to the data.

XII. Privacy and Confidentiality:

Participants' privacy and confidentiality will be safeguarded by using modern database management techniques and informed consent. Only authorized study personnel will have access to the data.

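### On the natural reading of Objective 3, differences between an adult's reported heights enter BMI change as noise; one height per adult would remove it.

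*Protocol*

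**What the plan says.** - **Purpose of height (Protocol, Section I, objective 3):** "Collect data on participant height change over 6 months to calculate body mass index (BMI". No age group is singled out.
- **Population (Section V.a):** "Male and female individuals diagnosed with PWS, 12 years and older". There is no upper age limit, so adults are included.
- **Timing (Section III, item 3):** "At 3 months and 6 months participants will answer a survey". Question 5 of that survey reads "Please record participant's height". No measuring method or number of readings is given. The list headed "Initial Survey at baseline only" does not include height.
- **Mode of reporting (Section VIII):** participants "will respond directly via text". No site measurement is described.
- **Weight (Section III, item 2):** collected "Once a week, every week, for 6 months".
- **Analysis (Section VII, item 1):** "Trends in weight and BMI change over 6 months". Item 2 adds a description of factors that could affect weight and BMI.

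The protocol has no rule for which height is the denominator of BMI at a given time, and no separate rule for adults.

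**The concern.** Height change can help to calculate BMI only if different heights are used at different times. For a 12- to 17-year-old that is right, because growth is real and must be reflected. For an adult, true height is effectively constant over six months, so a difference between two reports carries almost no information beyond reporting error. BMI divides by height squared, so a given relative error in height roughly doubles in BMI.

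What is at stake is precision. An adult whose weight has not moved could show a BMI gain or loss. The comparisons of BMI change by food access, activity, living situation and medication would also carry extra scatter that has nothing to do with those factors.

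This is separate from the lack of a baseline height. Adding a baseline height would serve the adolescents. If it were then used as the adults' baseline denominator, two separately erring heights would still stand in their six-month BMI change.

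**Working it through.** The protocol gives no figure for BMI, height, height error or variability of weight change, so there is nothing of its own to reproduce. The size below rests on stated assumptions.

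**Assumed inputs**
- Adult of 80 kg and 155 cm: BMI = 80 / 1.55² = 80 / 2.4025 = 33.3 kg/m2.
- Height-error SD per report, s: 0.5, 1 or 2 cm.
- Correlation of the two errors, rho: 0 first, then varied.
- SD of true six-month weight change: 3 kg or 5 kg.

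**Step 1. False BMI change with weight and true height fixed.**
SD = 2 × BMI × s × √(2(1 − rho)) / H. At rho = 0 this is 2√2 × 33.3 × s / 155 = 0.608 × s. Multiplying by 2.4025 gives the weight equivalent.

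| s (cm) | SD of false BMI change (kg/m2) | Weight equivalent (kg) |
|---|---|---|
| 0.5 | 0.30 | 0.7 |
| 1 | 0.61 | 1.5 |
| 2 | 1.22 | 2.9 |

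Simulation with 400,000 draws per scenario agreed with the formula to about 0.01 kg/m2. Across heights of 145 to 165 cm and BMI of 28 to 42, the SD is 0.24–0.41 at s = 0.5 cm, 0.48–0.82 at 1 cm and 0.96–1.64 at 2 cm.

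**Step 2. Inflation of the variance of BMI change.**
A 3 kg SD of weight change is 3 / 2.4025 = 1.25 kg/m2, and a 5 kg SD is 5 / 2.4025 = 2.08 kg/m2. Inflation = (false-change SD / true-change SD)². For example, at s = 1 cm and 3 kg it is (0.608 / 1.249)² = 0.24.

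| s (cm) | 3 kg, rho = 0 | 3 kg, rho = 0.5 | 3 kg, rho = 0.9 | 5 kg, rho = 0 |
|---|---|---|---|---|
| 0.5 | 6% | 3% | 0.6% | 2% |
| 1 | 24% | 12% | 2.4% | 9% |
| 2 | 95% | 47% | 9.5% | 34% |

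The false-change variance scales with (1 − rho). If the same known height is given twice, rho = 1 and the effect is zero.

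**Step 3. Effect on the mean.**
The simulated mean false change was within 0.01 kg/m2 of zero. Even if all 300 participants were adults, the standard-error component from height noise would be 0.61 / √300 = 0.04 kg/m2 at s = 1 cm and 1.22 / √300 = 0.07 at s = 2 cm. Smaller factor groups carry proportionately more.

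**Step 4. Where it can enter.**
Heights exist only at months 3 and 6, so a baseline BMI must borrow one of them. If the month-3 height is borrowed and the month-6 BMI uses the month-6 height, both errors enter the six-month change. If one height serves both ends, neither does, beyond a small rescaling.

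**Step 5. With one height per adult.**
BMI change becomes (W2 − W1) / H². Only a proportional error of about 2s / H remains: 2 × 1 / 155 = 1.3% of the change at s = 1 cm for a single reading.

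**The case against.** The strongest reply is that the protocol does not fix a denominator at all. A reader might infer that every adult BMI is divided by the height from the same survey, but no sentence says so. Derivation rules for BMI often sit in a SAP, and none is at hand. That limits the point without removing it. Objective 3 itself names height change as the input to BMI for everyone, and this has no meaning unless differing heights are used.

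Second, question 5 asks for height to be recorded, not measured. A caregiver who gives a known adult height twice repeats the same error and creates no false change. This stands, and it is why the figures must be shown over rho and not only for independent errors.

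Third, a reader might infer that the mean BMI trend is biased or that factor differences shrink. Neither follows. Random error in an outcome widens intervals but does not move the mean or attenuate group differences. A shift in the mean would need a systematic change in how height is reported, and the protocol gives no sign of one.

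Fourth, asking height again is not a mistake in itself. Adolescents need it, and the remedy uses the same reports. This also stands: the fault lies in applying height change to adults, not in question 5.

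**Conclusion.** The point holds as a matter of precision in a secondary quantity. Read naturally, Objective 3 lets disagreement between two reported adult heights count as BMI change. Under the assumed 80 kg and 155 cm, the false change has SD 0.30 to 1.22 kg/m2 for independent errors of 0.5 to 2 cm. That adds 6% to 95% to the variance of BMI change if true weight change has SD 3 kg, and 2% to 34% if it has SD 5 kg. These are upper figures: they fall in proportion to (1 − rho) and reach zero for a repeated height. Every input is an assumption, because the protocol supplies none.

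The documents do not support a claim that the mean BMI change is wrong or that the weight results are affected. The harm is confined to individual adult BMI changes and to noisier factor descriptions on BMI. It is worth correcting because the correction costs so little.

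**What to change.** - **Section VII, item 1:** state that for participants aged 18 or over a single height per person is used in every BMI value, namely the mean of that person's reported heights after implausible discrepancies have been checked. State that time-specific heights are kept for ages 12 to 17.
- **Checking:** discrepancies should be looked at in both directions. Querying only heights that fall would correct low errors, leave high ones, and push adolescent height change upward.
- **Section I, objective 3:** limit the height-change part to participants who are still growing.

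Question 5 can stay as it is. The cost is a short rule in the analysis section, a reworded objective, and follow-up of the few implausible height pairs. There are two downsides. Slight late growth in young adults is ignored, and adult BMI change becomes a rescaled weight change, adding little to the weight analysis. The second should be said openly when results are reported.

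### Weight and BMI trends are planned for everyone aged 12 and over with no age-group analysis or age-standardised measure, although the Background says weight change may depend on age

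*Protocol*

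**What the plan says.** Objective 1 (section I) is to "Perform a real-world study of weight changes over 6 months in PWS children and adults aged 12 and over". The inclusion criterion (section V.a) is "Male and female individuals diagnosed with PWS, 12 years and older". There is no upper age limit, and no strata or quotas by age.

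The Background (section II) states: "It has previously been shown that weight changes in PWS may depend on age- and nutritional stages". It adds that "larger datasets across different age groups, with frequent measurements, are required to fully understand real world data".

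Section VII lists two analyses. Item 1 is "Trends in weight and BMI change over 6 months". Item 2 is "Description of factors that could affect weight and BMI in this group, including food access, change in living situation, physical activity and medication". Neither item names a z-score, a percentile, percent change or an analysis by age group. Item 2 does not name age, sex or growth hormone.

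On data collection (section III), gender, age and growth hormone history are items of the survey headed "Initial Survey at baseline only". Height is not in that survey. It appears only in the survey sent at 3 and 6 months: "Please record participant's height".

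**The concern.** A participant of 12 may still be growing and an adult is not, so a kilogram gained over six months does not mean the same in both. In a growing adolescent it combines expected growth with any excess gain. BMI takes account of height but not of age or sex, so a change in BMI is not comparable across the two groups either.

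The study covers roughly the length of a clinical trial, in age groups likely to be recruited to hyperphagia trials. An overall six-month figure that moves with the proportion of adolescents who happen to enrol would be hard to use for that purpose. It would describe neither the adolescents nor the adults. The factor description has the same weakness: anything that goes with age, such as current growth hormone use, could appear related to weight change because younger participants are growing.

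The protocol itself raises age as a possible determinant of weight change, then leaves it out of the analyses it names.

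**Working it through.** The protocol gives no trend estimate, standard deviation, effect size, power or precision target. The 300 participants are a bare target, so there is no figure to reproduce. The calculations below are illustrations.

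**1. Growth carried into an overall mean weight change**

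Inputs, all assumed because the documents give none:
- p, the share of adolescents: 20% to 65%
- g, the growth-related gain over six months in adolescents: 0.5 to 2.5 kg
- growth-related gain in adults: 0 kg

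Suppose adults change by a on average and adolescents by a + g. The overall mean is then a + p × g. It lies p × g above the adult value and (1 − p) × g below the adolescent value. Values of p × g in kg:

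| p | g = 0.5 | g = 1.5 | g = 2.5 |
|---|---|---|---|
| 0.20 | 0.100 | 0.300 | 0.500 |
| 0.35 | 0.175 | 0.525 | 0.875 |
| 0.50 | 0.250 | 0.750 | 1.250 |
| 0.65 | 0.325 | 0.975 | 1.625 |

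The range is 0.10 to 1.63 kg. At p = 0.50 and g = 1.5, the overall mean is 0.75 kg above the adult value and (1 − 0.50) × 1.5 = 0.75 kg below the adolescent value. At g = 1.5, changing only the age mix from 20% to 65% adolescents moves the overall mean by 0.975 − 0.300 = 0.675 kg, with no change in either group.

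**2. BMI in a growing participant**

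Assumed starting point: 60 kg and 1.50 m, so BMI = 60 / 1.50² = 26.67 kg/m². Change = (60 + g) / (1.50 + h)² − 26.67, where h is height growth over six months, assumed 0 to 3 cm:

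| h | g = 0.5 kg | g = 1.5 kg | g = 2.5 kg |
|---|---|---|---|
| 0 cm | +0.22 | +0.67 | +1.11 |
| 1 cm | −0.13 | +0.31 | +0.74 |
| 2 cm | −0.48 | −0.05 | +0.38 |
| 3 cm | −0.82 | −0.39 | +0.03 |

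The change runs from −0.82 to +1.11 kg/m². BMI therefore absorbs part of the growth, and its change can go either way. What it lacks is a reference for age and sex.

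**3. Can the remedy be carried out on the data as collected?**

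- Age-group reporting: yes, because age is collected at baseline.
- Age and growth hormone as factors: yes, because both are in the initial survey. The follow-up medication item asks only about changes in the preceding three months, so unchanged growth hormone use would not show there.
- Standardised weight: yes, if age is recorded precisely enough for a growth standard. The survey item says only age.
- Six-month BMI change, raw or standardised: no. It needs a baseline height, and height is first asked at 3 months. For adults the 3-month height could stand in if adult height is assumed stable; for participants still growing it cannot.

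**The case against.** A reader might infer that the protocol fixes one pooled trend in raw units. The text does not support that. Item 1 states no model, scale or single trend, and the Background's interest in different age groups points, if anything, towards a breakdown by age. No section says the groups will be pooled, and none says they will be separated. Strata and covariates are also often left to an analysis plan, which may exist here. That part of the objection stands, and it limits the point to what an overall trend would mean if reported.

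A reader might also infer that age is excluded as a factor. It is not. The list in item 2 is open-ended, and medication could be taken to cover growth hormone. Likewise, the Background says weight change may depend on age, not that it does.

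It would also be too strong to say that the study counts normal growth as weight gain caused by the syndrome, or that weight and BMI are equally affected. The aim is descriptive, no section attributes observed gain to the syndrome, and observed change is itself of interest in a trial population. BMI partly corrects for growth, as the second table shows.

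Finally, the kilogram figures rest wholly on assumptions, and at the low end the effect is trivial.

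What the objection does not remove is that the only analyses named leave out a determinant the protocol itself raises, for a population in which the two outcomes do not carry one meaning. Nor can an analysis plan supply a baseline height that was never asked for.

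**Conclusion.** The point holds in a limited form. The protocol names weight and BMI trends for ages 12 and over with no age-group analysis or age-standardised measure, and does not name age among the factors, despite its own Background. An overall kg or BMI trend would mix adolescent growth with adult change and would depend on the age mix enrolled.

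The size cannot be derived from the documents. About 0.1 to 1.6 kg over six months follows only from the assumed adolescent shares and growth-related gains, with no growth-related gain in adults. The firmest part needs no assumption about growth: the protocol as written collects no baseline height, so it cannot deliver a six-month BMI change on any scale.

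This should be changed because it is cheap and makes the results easier to interpret. It is not evidence that a pooled analysis has been chosen.

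**What to change.** In VII, item 1, state that the six-month trend will be reported separately for 12-17 years and for 18 years and over. For participants still growing, give age- and sex-standardised weight and BMI alongside the raw values, and name the growth reference used. For adults, add percent weight change. If an overall figure is also given, show the age mix with it.

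In VII, item 2, add age and growth hormone status to the factors. Both are already collected.

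In section III, add height to the initial survey and record age precisely enough for growth standards (for example, in years and months).

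The cost is one extra baseline question, a more exact age item, some added analysis, and wider intervals within each age band. For scale, with an assumed SD of 5 kg for six-month change, the 95% half-width 1.96 × SD / √n is 0.57 kg for all 300 participants and 0.80 kg for a band of 150. With SDs of 3 and 7 kg, it goes from 0.34 to 0.48 kg and from 0.79 to 1.12 kg. These assume complete data and equal bands.

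### Diet is named in primary objective 2 but asked in no survey, and food access is asked only as change, so weight trends cannot be related to diet or to a constant level of food access

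*Protocol*

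**What the plan says.** Protocol Section I, objective 2: "Study factors that could directly or indirectly affect weight change such as diet, medication, food access and environment". It is listed as one of three primary objectives.

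Section II gives the reason, "Weight may also be influenced by living situation, diet, medication and access to food". It then says "we will also survey participants on diet and medication changes and food access", with the aim to "study the extent to which these may play a role in any observed weight change".

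Section III itemises what is collected. The first survey is headed "Initial Survey at baseline only" and has five items: diagnosis by blood test, gender, age, growth hormone, and how often the person was weighed. The growth hormone item ("Does the person receive growth hormone (GH) therapy") goes on to past use, age at start and duration. The survey at 3 and 6 months also has five items. The first begins "Has there been any change in the living situation for the person with PWS in the last 3 months". The next two ask whether food access and activity went up, went down or did not change. The fourth asks whether medication changed, and drugs are listed only after a yes. The fifth is height.

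Section VII item 2 plans: "Description of factors that could affect weight and BMI in this group, including food access, change in living situation, physical activity and medication".

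**The concern.** The objective, the data collection and the analysis do not name the same factors. Diet is promised twice and never asked. Food access is promised as a factor in its own right, but only its movement during the study is asked.

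This bears on a primary objective. It is also not a detail that an analysis plan could settle: such a plan can choose models and subgroups, but it cannot recover an exposure that no participant was asked about. No other source is described. The Global PWS Registry appears in Section V only as a recruitment channel, with no data linkage.

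**Working it through.** The protocol states no figure to reproduce here. The check matches each named factor against each listed question.

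| Factor | Objective 2 | Section II | VII.2 | Baseline level asked? | Asked at 3 and 6 months? |
|---|---|---|---|---|---|
| Diet | named | named, to be surveyed | not named | no | no |
| Food access | named | named, to be surveyed | named | no | change only |
| Medication | named | named as a factor; survey of changes promised | named | growth hormone only | change only |
| Physical activity | not named | not named | named | no | change only |
| Living situation | at most under environment | named as a factor | named as change | no | change only |

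**Counts.** Diet: 0 of 5 + 5 = 10 listed items. Level of food access: 0 of 5 baseline items. Level of activity: 0 of 5. Level of medication: 1 of 5, and only for growth hormone. Of the five follow-up items, four concern exposures, and 4 of 4 ask about change only.

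**Diet.** The Section II phrase can be read as diet or as changes in diet. Either way, no item matches. Food access cannot stand in for diet, because objective 2 and Section II list the two separately.

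**Food access.** Take one participant whose access is open throughout and one whose access is restricted throughout. Both report no change at 3 and at 6 months, and neither has a baseline value, so their exposure records are identical. If a share p of the unchanged group has open access, the mean weight trend in that group is

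p × (trend under open access) + (1 − p) × (trend under restricted access).

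The data give only the sum. Neither p nor the two trends can be separated. A report of increased access does not show the level from which it rose.

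**Medication and activity.** The structure is the same. A stable user of a drug other than growth hormone and a non-user both answer no. A report of a stop or a dose change implies earlier use of that drug, but only for people who changed. The activity question cannot separate constantly active from constantly inactive participants.

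**What remains estimable.** Weight trends can be compared between participants who report a change and those who do not, for food access, activity, medication and living situation. They can also be related to growth hormone use at baseline, whether or not that use changes later.

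**The case against.** The strongest reply is that change was a deliberate and coherent choice. Objective 2 speaks of factors affecting weight change, and VII.2 promises only a description. Asking about changes over the same six months as the weights fits that purpose. Nowhere does the protocol say that trends will be compared across levels of an exposure, so a wish for levels could be reviewer preference.

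Much of this stands for two factors. For medication, Section II promises to survey changes only, so the question matches that section and falls short only of the broader wording in objective 2 and VII.2. Activity is named in VII.2 alone, so the argument from a primary objective does not reach it by name. Living situation is not affected, because VII.2 itself limits it to change.

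The reply is weaker for food access. Objective 2, Section II and VII.2 all name it without that limit, and VII.2 does apply the limit to the neighbouring factor, living situation. Without a level, even a plain description of food access in this group cannot be given. For diet the reply fails, since neither level nor change is asked.

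A reader might infer that objective 2 can be answered only for factors that changed during the study, or that the change-based analysis is invalid. The documents support neither. Growth hormone is recorded as a baseline level, and comparison against unchanged participants is valid, though narrower than the objective's wording.

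**Conclusion.** The point holds in two graded parts. First, diet is an internal contradiction: it is named in a primary objective and promised in Section II, but it appears in none of the ten survey items and not in VII.2. The study cannot address it. Second, food access has no level at any time point, so weight trends cannot be related to access that stayed constant. Activity and medication other than growth hormone have the same limit, but only as a secondary remark.

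The weight and BMI trends planned in VII.1 are unaffected. No loss of precision is claimed, because the protocol gives no expected share of participants reporting a change. The conclusion assumes that the items listed in Section III are the full surveys. Question wording and response options are given for most of them, which supports that reading. The protocol should be corrected, since data not collected during the study cannot be supplied at analysis.

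**What to change.** 1. **Diet.** Either add one baseline diet item with a matching change question at 3 and 6 months and name diet in VII.2, or remove diet from objective 2 and Section II.
2. **Food access.** Add a baseline level, aligned with follow-up question 2, which now combines home and outside. Either ask the two settings separately at baseline and split question 2 in the same way, or use one combined item at all time points.
3. **Optional.** Add one-time baseline items on usual activity and current medications.
4. **VII.2.** Reword along these lines: *Description of weight and BMI trends by baseline level of each factor where collected, and by reported change at 3 and 6 months. These are observational associations and are open to confounding.*

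If no baseline items are added, limit objective 2 and VII.2 to reported changes in food access, activity, medication and living situation, keep baseline growth hormone use as a level, and remove diet. This is a wording change with no added burden.

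**Cost.** Current load per participant: 5 baseline items + about 26 weekly weights + 2 × 5 follow-up items = about 41.

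- Diet: 1 + 2 = 3 items.
- Food access: 1 item if combined; 2 + 2 = 4 if split.
- Diet plus food access: 4 items (4/41 = 9.8%) to 7 items (7/41 = 17.1%).
- With both optional items: 6 (6/41 = 14.6%) to 9 (9/41 = 22.0%).

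Item counts understate the effort for medication. A drug list takes longer than a weekly weight reply and needs coding of free text, as the follow-up drug list already does, but for more people. Under Sections XIII and XIV, participants bear their own text charges and are not reimbursed, so the optional items should be weighed against that.
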